#### 11.4.4 Interim analyses

An interim safety analysis will be performed after the first 250 subjects have been randomized and reached the 9-months-old visit; a safety report detailing the results of the analysis will be compiled for the DSMB and the CCER.

#### 11.4.5 Safety analysis

AE and SAE will be reported by group, using standard descriptive statistics (frequencies, medians and interquartile ranges, or means and standard deviation) for each AE of interest (see section 10)

- prevalence
- day of onset
- size (e.g. for redness or induration)
- duration
- severity (using standardised grading scales)
- causality with the intervention
- treatment
- resolution

The analyses will be done thrice, in collaboration with the Clinical Research Center at Geneva University Hospitals, at the same time of the interim analysis, the same time of the primary analysis, the same time of the final analysis.

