## 4.4 Safety Objectives

### Stage A

**AIM10:** Determine the safety of early MMR vaccination.

*Hypothesis:* MMR vaccine is safe and well-tolerated at 6 months of age, inducing similar safety profile than when given later on.

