### 5.4 Safety Outcomes

**AIM10: Vaccine safety:** occurrence and severity of local and systemic adverse events, as well as any serious adverse events, by systemic organ class, preferred term, severity using toxicity grading scale, and relationship to the intervention from day 0 to day 42 post MMR.

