**Part 2 only: blood will be collected** (maximum 15 ml), in subjects whose parent accepted blood collection, for the laboratory tests listed in section 9.2.2. This is done after informed consent is obtained but prior to randomisation. In the eventuality that the blood collection fails, the subject will be considered as not consenting to blood tests (participation to Part 1 only), given that the laboratory analysis in Part 2 cannot be made in the absence of a baseline blood sample.

**Randomisation** in the trial, using a web-based randomisation procedure integrated into REDCap, stratified by consent to blood tests (yes/no), in randomly permuted blocks of variable length (4 or 8), enabling to prevent predictability of intervention assignments.

**Distribution of the vaccination plan** according to the group the subject has been randomised to.

**Group M.C. or M.M. only: MMR vaccination (first dose)**; Subjects randomised to the Group M.C. or M.M. (modified schedule for the 1st MMR dose) will receive one dose of MMR vaccine. After reconstitution of the vaccine by adding the entire content of the pre-filled syringe of solvent to the vial containing the powder, the vaccine (0.5 ml) will be injected intramuscularly in the deltoid region or in the anterolateral area of the thigh. The subject will be distracted during the injection, in order to minimise the pain. The subject will remain under close observation for 20 minutes after the injection.

**Group C.M. or C.C. only: No vaccination**; Subject randomised to the Group C.M. or C.C. (current schedule for the 1st MMR dose) will not receive any vaccine at 6 months.

**Vaccine diary** will be presented to the parents, who will be instructed to fill it for the next 42 days.

**Fortnightly questionnaire** will be presented to the parents, who will be instructed to fill them every 2 weeks for the next 18 months.

**Contact details** will be given to the parent, consisting in an emergency card with a phone number to call in case of questions about the trial or upon occurrence of any adverse event.

**Scheduling** next visits.

Once the subject and their parent have left:

**Data entry** will be checked by the investigator to ensure that no information is missing. Parents could be contacted if any data is missing.

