### 9.3.3 Visit 2: Follow-up, 9 months of age ( $t_{+3m} \pm 2$ weeks)

**Review of the fortnightly questionnaires** by investigators, together with the parent, to ensure concordance and the absence of missing data; instruction to continue to fill them every 2 weeks until the subject is 24 months old.

**Review of vaccine diary**, by investigators, together with the parent, to ensure concordance and the absence of missing data; instruction to fill a second vaccine diary the next 42 days.

**Review of vaccination records**, by investigators, to ensure that all is in order. Review with the parent the vaccination plan and ensure it is well understood.

**Overview of the next steps of the trial** by investigators, using the study flow chart to ensure correct comprehension of the parent, with the possibility for parents to ask any question.

**Target clinical examination** will be performed if needed, to ensure that there is no temporary contra-indication for the vaccination (e.g. if the child is sick, the vaccination can be delayed a few days until the illness resolves) or for the blood test (e.g. if the child is sick or recovering, the visit can be delayed a few days until the illness resolves, as it might influence the laboratory test).

**Eczema assessment** will be performed, using SCORAD score.

**Part 2 only: blood will be collected** (maximum 15 ml), in subjects whose parent accept blood collection, for the laboratory tests listed in section 9.2.2. In the eventuality that the blood collection fails or if parents does not accept blood collection at this visit, the subject will remain in Part 2, as they have already provided a baseline blood and further blood collection might succeed.

**Group C.M. or C.C. only: MMR vaccination (first dose)**; Subject randomised to the Group C.M. or C.C. (current schedule for the 1st MMR dose) will receive one dose of MMR vaccine. After reconstitution of the vaccine by adding the entire content of the pre-filled syringe of solvent to the vial containing the powder, the vaccine (0.5 ml) will be injected intramuscularly in the deltoid region or in the anterolateral area of the thigh. The subject will be distracted during the injection, in order to minimise the pain. The subject will remain under close observation for 20 minutes after the injection.

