## 10.1.1 Definition and assessment of (serious) adverse events and other safety related events

### 10.1.1.1 Definition of adverse event

An **Adverse Event (AE)** is any untoward medical occurrence in a patient or a clinical investigation participant administered a pharmaceutical product and which does not necessarily have a causal relationship with the study procedure. An AE can therefore be any unfavourable and unintended sign (including an abnormal laboratory finding), symptom, or disease temporally associated with the use of a medicinal (investigational) product, whether or not related to the medicinal (investigational) product. [ICH E6 1.2]

For the period of vaccination to 42 days post vaccination only, the following solicited adverse events are non-serious adverse events of interest for this study; they will be collected using vaccine diary.

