#### 10.1.1.1.3 Unsolicited adverse events

Unsolicited adverse events will be recorded during study visits, and through consulting with the treating paediatrician and the medical record, or if the subject's parent spontaneously contact the investigator. They are defined as an adverse event of interest and will be reported as such only if they began within the first 42 days following the intervention and if the causality assessment deems the event to be possibly, probably or definitely associated to the intervention.

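### AIM10 asks whether MMR at 6 months is as well tolerated as later MMR, but solicited systemic events are counted only after MMR, so the first-dose comparison mixes vaccine effect with age and omits the randomised unvaccinated control at 6 months

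*Protocol*

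**What the plan says.** Section 4.4 (AIM10) is comparative: "MMR vaccine is safe and well-tolerated at 6 months of age, inducing similar safety profile than when given later on". Section 5.4 fixes the outcome as local, systemic and serious events, with severity and "relationship to the intervention from day 0 to day 42 post MMR"; section 9.2.4 repeats the window. Section 10.1.1.1 narrows the solicited items: "For the period of vaccination to 42 days post vaccination only, the following solicited adverse events are non-serious adverse events of interest". Section 10.1.1.1.3 counts unsolicited events "only if they began within the first 42 days following the intervention", and only if they are judged at least possibly related. Section 11.4.5 then says "AE and SAE will be reported by group, using standard descriptive statistics".

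Diary collection is described more broadly. At Visit 1 (9.3.2) the vaccine diary "will be presented to the parents, who will be instructed to fill it for the next 42 days". No group is named, although the neighbouring vaccination items are marked as applying to certain groups only. Visit 2 (9.3.3) adds an "instruction to fill a second vaccine diary the next 42 days", and Visit 3 (9.3.4) a third, although each child receives two MMR doses. Against this, footnote f of the schedule (Study Schedule and 9.1) and section 9.2.4.1 tie the follow-up to vaccination.

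Section 10.1 collects serious adverse events for the whole study, from consent onwards.

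**The concern.** The two first-dose windows lie three months apart in age. Table 4 of the protocol itself lists factors that change after randomisation, such as childcare attendance, stopping breastfeeding and introduction of solids. Background fever, irritability, vomiting, diarrhoea or rash may therefore differ between the windows for reasons unrelated to the vaccine. Randomisation does not help, because the groups are observed after MMR at different ages.

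The protocol recognises this for the laboratory outcomes: section 9.2 relies on the control group to tell maturation apart from vaccine effects. The safety section does not use the same device. A reader who checks AIM10 against the by-group table could conclude that the early dose is better or worse tolerated when only the background has moved.

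The interim safety report (11.4.4) is due once the first 250 children have reached the 9-month visit. By then the 6-month diaries are finished, while the latest C children have only just had MMR. The most complete comparison for the DSMB at that point would be the 6-month one, whose control half falls outside the event definition.

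**Working it through.** **1. The plan's own figure.** No sample size, margin or power is given for AIM10. The primary calculation (11.2) reproduces. The difference is 0.30 × 0.29 = 0.087 and the SD 0.32, so 2 × (1.96 + 0.842)² × 0.32² / 0.087² gives 213 per arm. Then 213 / 0.85 = 251 per arm, 502 in total against 500 stated. I use only the 0.29 rate and about 0.85 × 250 = 212 children per first-dose arm.

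**2. Diaries, if the visit text is followed.**

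| Diary | M.C. + M.M. (250) | C.M. + C.C. (250) |
|---|---|---|
| 6 months | after MMR: counted | no vaccine, MMR-naive: not counted |
| 9 months | no vaccine at this visit, MMR about 3 months earlier: not counted | after MMR: counted |
| 12/13 months | after MMR: counted | after MMR: counted |

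Of 3 × 500 = 1500 diaries, 1000 follow a dose and 500 do not. The first-dose comparison that remains is the diagonal of the first two rows.

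**3. Background in 42 days.** 42 / 30.44 = 1.38 months, and 0.29 × 1.38 = 0.40 expected respiratory infections. Under a Poisson count, 1 - exp(-0.40) = 33% of children have at least one. This is a stand-in: the protocol gives no background rate for fever or the other solicited items, and none by age.

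**4. Raw contrast when the vaccine does the same at both ages.** Assumptions: 33% background at 9 months; a vaccine-caused event with probability 10%, independent of background; 6-month background rate 0.7 to 1.3 times the 9-month rate. Risk after MMR is 1 - (1 - background) × 0.90.

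| Rate ratio | Background, 6 m | After MMR, 6 m | After MMR, 9 m | Raw difference |
|---|---|---|---|---|
| 0.7 | 24.4% | 32.0% | 39.7% | -7.7 points |
| 1.0 | 33.0% | 39.7% | 39.7% | 0 |
| 1.3 | 40.6% | 46.5% | 39.7% | +6.8 points |

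With 9-month background from 15% to 50% and vaccine probability from 5% to 20%, the raw distortion at these two ratios is about 3 to 11 points, in either direction.

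**5. Contrast within the 6-month diary.** M minus C equals 0.10 × (1 - background): 7.6, 6.7 and 5.9 points for the three rows. That is the vaccine's excess at 6 months. Background cancels because the children are randomised and observed at the same age. At 40% risk and 212 per arm, the 95% half-width is 1.96 × √(2 × 0.4 × 0.6 / 212) = 9.3 points, the same as for the raw contrast.

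**6. Difference of the 6- and 9-month differences.** In step 4 it is within 1 point of zero. It fails if the trial's own hypothesis is right. Take equal background of 33% at both ages, an added 10 points from vaccination, and a 30% rate reduction (33.0% to 24.4%) that starts with the dose and lasts through the 9-month diary. Then:
- 6 months: 34.4 - 33.0 = 1.4
- 9 months: 34.4 - 24.4 = 10.0
- difference: -8.6 points, although the raw contrast is 34.4 - 34.4 = 0

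Its half-width is 9.3 × √2 = 13.2 points, or 15.0 with a within-child correlation of 0.3.

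**The case against.** The strongest case against is that 11.4.5 is descriptive, P<.05 is set for the primary outcome only, and table layout belongs in the SAP. That is right about testing: turning step 4 into a rate of falsely significant trials would attribute to the plan a test it does not contain. It does not dispose of the point, because the event window is fixed in sections 5.4 and 10.1.1.1 of the protocol. A table laid out under that definition has no unvaccinated half.

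Several stronger readings are tempting and are not supported:
- **That all safety is counted only after MMR.** Serious events are collected throughout, so they can be compared concurrently by group. Sections 5.4 and 10.1 should still agree on their window.
- **That the whole reactogenicity table is background illness.** Four of the 13 solicited items are local reactions. Day of onset and causality are reported, and unsolicited events need at least possible causality.
- **That the early dose will look falsely better.** The documents give no age gradient, so even the sign is unknown.
- **That unvaccinated controls exist at both ages.** M children at 9 months had MMR about three months earlier, and AIM1 and AIM6 suppose a lasting effect of that dose. Step 6 shows what this can do.
- **That the control diaries are certain to be collected.** The visit text says so; footnote f and sections 9.2.4.1 and 10.1.1.1 point the other way.

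**Conclusion.** The point holds for solicited systemic events after the first dose. AIM10's hypothesis compares ages, and the fixed window plus by-group description leaves a contrast in which vaccine effect and age cannot be separated. A distortion of several points either way is plausible (about -8 to +7 in the main illustration). That size rests on assumed age ratios, an assumed vaccine excess and a respiratory rate used as a stand-in.

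The 6-month diary contrast is randomised, concurrent and MMR-naive in its control half, and it is available if the visit text is followed. It estimates the net effect of vaccination at 6 months, including any early non-specific protection (the 1.4 points in step 6). It does not by itself show similarity to the later dose; the documents offer no clean control for that. If diaries were in fact given only after vaccination, this control would be lost and the confounding by age would remain.

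**What to change.** 1. Reconcile footnote f and sections 9.2.4.1 and 10.1.1.1 with 9.3.2 and 9.3.3, and state which groups complete each diary.
2. In 5.4 (and 9.2.4 and 10.1.1.1), extend the solicited-event window to the same 42 days after the 6-month visit in C.M. and C.C.
3. In 11.4.5, add for each solicited systemic event the 6-month diary risk difference, M.C. + M.M. minus C.M. + C.C., with a 95% confidence interval. Include it in the interim report.
4. Keep the by-group post-MMR table as description, and state that its 6- versus 9-month contrast is confounded by age.
5. A 9-month contrast (C vaccinated minus M not vaccinated at that visit) may be shown descriptively, noting the earlier MMR in the M groups. Do not make the difference of differences the answer to AIM10.

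The cost is a wording change and one extra table, with no new visits or data if the visit text is followed. The trial is open-label without placebo, so parents' knowledge of allocation can still affect what they record. Intervals of about ±9 points will not exclude modest excesses.

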#### 11.4.6 Deviation(s) from the original statistical plan

A detailed statistical analysis plan will be written as a separate document. It will be further updated as needed. All deviations from the planned analyses will be recorded in the trial master file, and reported and justified at the end of the trial.

### 11.5 Handling of missing data and drop-outs

Efforts will be made to minimise missing data, with regular check for data completeness during study visit and through contacting the treating paediatrician. Moreover, our team is both flexible and mobile (with experience in performing home visit or phone call when needed), as most data can be collected through self-reporting using telephone and email communication, even if not ideal.

Missing data, including those due to study dropouts, will be marked as such in interim analyses, the clinical study report, and any published manuscripts reporting trial data. Missing data will be taken into consideration using several methods, among them responder analysis (worst-case/best-case scenarios), complete-case analysis (modified ITT) and potentially multiple imputation. These sensitivity analyses will be used if required to validate study findings and will be detailed in the statistical analysis plan.

## 12. QUALITY ASSURANCE AND CONTROL

Approved SOPs will be used for all procedures, including clinic visit, phone calls, and laboratory procedures. The PI is responsible for proper training of all involved study personnel.

## 12.1 Data handling and record keeping / archiving

Data will be collected in electronic Case Reports Form (eCRF) in REDCap. All study related documents will be archived electronically on the secured server of the HUG. The full details of the data management will be provided in a data management plan.

### 12.1.1 Case Report Forms

All questionnaires answered by parents will be directly entered in REDCap through eCRF; these include baseline questionnaires, fortnightly questionnaires and vaccine diaries.

Investigators will also use eCRF during study visits or when calling the treating paediatrician.

REDCap is suitable for direct data entry as it is a secure, web based software platform designed to support data capture for research studies, as it provides an intuitive interface for validated data capture and has audit trails for tracking data manipulation and export procedures; access to the database is restricted by unique password and username.

On project-specific documents, participants are only identified by a unique participant number. The participant identification list will be stored by the principal investigator and will be protected from unauthorised or accidental disclosure by password. Only de-identified data will be used. Published data will summarise group outcomes only, individual study participants will not be identified.

### 12.1.2 Specification of source documents

For this trial source documents are original documents, data, and records that can help for the completion of the eCRF, keeping in mind that most CRF will be completed directly by the parent or the investigator without any source document. In this particular setting, source documents may include, but are not limited to: PICF; clinical notes (medical history, vital signs, physical examination, AE data, and concomitant medication and vaccination details) from investigators, treating paediatrician, or the subject's medical record; laboratory records; paper CRF vaccine diaries (e.g. rescue CRF used when completion of eCRF is impossible); vaccination record; and any correspondence. All source data and paper CRFs will be stored securely.

### 12.1.3 Record keeping / archiving

All study documents must be archived for a minimum of 10 years after study termination or premature termination of the clinical trial. The Investigator will maintain appropriate medical and research records for this trial, in compliance with ICH E6 GCP and regulatory and institutional requirements for the protection of confidentiality of volunteers. The Principal Investigator, co-investigators and clinical research nurses will have access to records. Investigators will permit monitors, ethical and regulatory agencies to examine (and when required by applicable law, to copy) clinical records for the purposes of monitoring, quality assurance reviews, audits and evaluation of the study safety and progress.

Data will be archived at HUG's Platform for clinical research in paediatrics, gynaecology and obstetrics. At the end of the project, the entire database will be archived in a reusable format. Archives encompass all raw data, meta-data, transformed data, transformation operations, deviations, version history, and audit trails. Redeployment of the entire database is therefore possible whenever needed. The comprehensive archive will remain property of the Sponsor-Investigator.

## 12.2 Data management

The Principal Investigator will have the responsibility for overseeing the reception, entry, cleaning, querying, analysis and storage of all data that accrue from the study by designated persons. Data management will be performed by the Platform of clinical research in Paediatric, Obstetrics and Gynaecology, in collaboration with the UIC (Unité d'Investigation Clinique), a unit which is part of CRC (Centre de Recherche Clinique / CTU) at the HUG (Hôpitaux Universitaires de Genève) and the Faculty of Medicine UniGE (Geneva University).

For each set of data, quality control and triggers to computerised logic and/or consistency checks will be systematically applied in order to detect errors or omissions. Standard operating procedure (SOP) will be used to standardise data collection, to ensure reliability and consistency. All study personnel will be instructed, trained and supervised on a regular basis to correctly collect and enter data into the electronic database. Subjects' questionnaires (baseline questionnaires, fortnightly questionnaires and vaccine diaries) will be directly filled up by the participants' parents through computer-assisted questionnaires (eCRF). Answers from parent's questionnaires are directly linked to the REDCap database which will minimise errors in data collection. After integration of all corrections in the complete set of data, the database will be locked and saved before being released for statistical analysis.

### 12.2.1 Data Management System

The UIC is certified ISO 9001/2008, and the unit guarantees best practices in the field of clinical data management.

All data and applications are physically stored in dedicated data centre on HUG premises. The physical hardware consists of enterprise-grade servers, networking, and storage solutions from tier 1 vendors and trustworthy and stable GNU/GPL solutions.

Data are physically stored in a MySQL ver.14 RDBMS (Relational Database Management System) using a dedicated CDMS software (Clinical Database Management System). This CDMS is a central Web-based system consolidating all CRF related data, whether the project is mono or multi centric.

All applications are hosted on certified virtual servers running Red Hat Linux Enterprise in a VMWare ESX environment. There are several dedicated servers for each system, ensuring separation between the testing / pre-production environment and the production environment. System updates are applied only after validation in the pre-production environment.

HUG infrastructure is under the responsibility of DSI (Direction des Systèmes d'Information at HUG). All exploitation, monitoring and backups operations are performed by DSI, in accordance with UIC policies.

All systems and applications are continuously monitored. Appropriate measures are automatically taken whenever an alert is issued.

Backups operations are performed by the DSI service at HUG, in accordance with UIC policies. Frequent backups are performed using the best enterprise backup solutions at HUG and are physically stored in a fire-proof safe. Backup strategy comprises an optimised hourly, daily, monthly, and yearly retention plan:

- Server backups (DSI): 1x differential per day (14 days retention, with mirroring), 1x full every month (retention 12 months), annual (preserved infinitely)
- Database backups (UIC): hourly, (retained 24 hours), daily (retained 2 months), monthly (preserved infinitely)

